10.2 Safety Review

Both the risks listed in Section 6.1 and unknown risks will be monitored as follows:

Adverse events will be monitored from the time of study enrollment until the end of participation. Adverse events will be monitored by medical staff using the “adverse events” CRF. Adverse event monitoring will be conducted at each study visit from the time of consent. Subjects will be given a wallet card with a 24/7 telephone number in the event that there are adverse effects which the subject would like to consult with medical staff prior to the next scheduled visit. Adverse events will be assessed if at any point in the study a subject uses this 24/7 emergency phone contact. If a subject has an ongoing SAE or unanticipated problem at the time that the subject completes all study procedures, Adverse Event assessment will continue until satisfactory resolution (either resolved or stabilized and is not expected to resolve in the near term) of the event or problem.

For each recorded AE or SAE, the study MD staff or study nurse will assess expectedness based on the known published side effect profile for exenatide. The study MD staff or study nurse will also assess severity based on the following criteria:

Mild: An event that is usually transient, requiring no special treatment, and does not generally interfere with the subject's daily activities.

Moderate: An event that interferes with usual activities of daily living, causing discomfort but poses no significant or permanent risk of harm to the subject. The event is usually ameliorated with additional specific therapeutic intervention.

Severe: An event that interrupts usual activities of daily living or significantly affects clinical status. The event poses a significant risk of harm to the subject and hospitalization may be required, and typically requires intensive therapeutic intervention.

Life-threatening An event that puts the subject into imminent risk of death without intervention.

The study MD staff or study nurse will assess AE/SAE relationship to the investigational product based on the following criteria:

Unrelated: The subject did not receive the investigational product, the temporal sequence of the AE/SAE onset relative to administration of the investigational product is not reasonable, or there is another obvious cause of the AE/SAE.

Unlikely:	There is evidence of exposure to the investigational product or there is another more likely cause of the AE/SAE.
Possible:	There is evidence of exposure to the investigational product, the temporal sequence of the AE/SAE onset relative to administration of the investigational product is reasonable, but the AE/SAE could have been due to another equally likely cause.
Probable:	There is evidence of exposure to the investigational product, the temporal sequence of the AE/SAE onset relative to administration of the investigational product is reasonable, and the AE/SAE is more likely explained by the investigational product than by any other cause.
Definite	There is evidence of exposure to the investigational product, the temporal sequence of the AE/SAE onset relative to administration of the investigational product is reasonable, the AE/SAE is more likely explained by the investigational product than by any other cause, and the AE/SAE shows a pattern consistent with previous knowledge of the investigational product or investigational product class.

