Design/Methodology:	This is a double-blind, randomized, placebo-controlled, crossover design trial that will test the effect of exenatide on alcohol self-administration and craving following a priming dose of alcohol. An established human laboratory self-administration procedure will be followed. Each subject will complete up to 4 clinic visits over a period of up to 38 days of participation. Study participation is comprised of a baseline assessment, alcohol self administration Trial 1, and alcohol self administration Trial 2. The volume of alcohol consumed during alcohol challenge trials 1 and 2 will be used to test the effect of exenatide on alcohol consumption. Craving measures (AUQ and VAS) collected during the self-administration trials will be used to test the effect of exenatide on alcohol craving.
Total Study Duration:	The entire study will take 24 months to complete.

Subject Participation Each subject's length of participation will be up to 38 days.
Duration:

3 Background/Rationale & Purpose

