Risks of alcohol self-administration

There is a potential risk of increased alcohol consumption following the alcohol self-administration experiment, but studies of subjects who have completed the alcohol self-administration procedure indicate that this is rare. Social drinkers who completed an alcohol self-administration study were not found to have increased risk for problem drinking 6 weeks after completing the self-administration study⁶¹. Similar results were found for alcohol dependent subjects 3 months after participation in a study testing the effects of naltrexone on alcohol self-administration⁶². Young social adult drinkers also did not exhibit an increase in real life drinking 6 weeks after the completion of intravenous alcohol self-administration experiments⁶³.

Subjects may reach a level of intoxication that is uncomfortable to them. If a subject consumed all eight drinks that were available to them during the two one-hour alcohol Challenge Trials, there is a possibility that they could reach an estimated peak BAC of 0.09 to 0.13g/dl taking into account the rate of metabolism of 0.010 to 0.020 g/dl per hour⁶⁴. This risk is unlikely to be a problem because we are recruiting subjects who routinely engage in binge drinking and have likely developed some tolerance to alcohol. The alcohol self-administration paradigm that we have chosen does not include any coercion, inducements, or pressure to consume more alcohol than subjects feel comfortable consuming. There are no experimental manipulations that would increase drinking (e.g., heavy-drinking confederate, anxiety manipulation). In fact, in this study design there are inducements for subjects to not drink beyond the initial priming dose. Subjects will receive monetary incentives for each drink that they do not consume. To reduce the risk of injury or harm after the subject has been discharged from self-administration laboratory, we will require that subjects have a plan for transportation that does not involve the subject driving. Subjects must have a BAC below 0.04 g/dl prior to discharge from the alcohol self-administration trials.

Risk of loss of confidentiality

There is some risk that health information collected as part of this study could be seen by unauthorized individuals. Every effort will be made to minimize this risk and protect subject confidentiality.

Adequacy of Protection against Risks

A) Recruitment and Informed Consent

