The study number will be preprinted on each injection pen. The label will include the drug name the subject number, storage conditions, the 24/7 phone number of the clinical site, and places to record the subject number and the date dispensed. Additional fields may be added to this label to meet any regulatory requirements as determined by IPS.

Medication Blinding/unblinding

Study medication will not be blinded. Medication will be administered by GCRUstaff who are not part of study staff who perform data collection. The Study PI and study staff will be blinded to study medication. The PI and study physician(s) will make the decision to un-blind the identity of the study medication in the event that the study blind needs to be broken to make medical decisions regarding subject treatment.

Medication accountability

The site principal investigator (PI) or designated study personnel will maintain a log of all study medication and record of dispensing of all medication to the subject.

9 Study Procedures

Study Overview: Each subject will complete 3 clinic visits over a period of up to 28 days of participation. Study participation is comprised of a baseline assessment, alcohol challenge Trial #1, and alcohol challenge Trial #2.

Baseline assessment: Prior to the visit, subjects will complete a COVID-19 symptom screening questionnaire following standard of care procedures. If the subject does not complete the screening questionnaire before arriving in clinic, study staff will administer the questionnaire outside of the clinic at a 6-foot distance. If the subject answers 'yes' to any question about known COVID symptoms, their in-clinic visit will be cancelled and they will be advised to contact their PCP and/or get tested at a testing center. Consenting subjects will undergo a general medical screen, physical examination, and electrocardiogram. Drinking will be assessed using

The Effects of Exenatide, a GLP-1 Agonist, on Alcohol Self-Administration in Heavy Drinkers
Version 1.8 10.5.20

the Time-Line Follow-Back (TLFB)⁴⁵, and alcohol withdrawal using the Clinical Institute Withdrawal Assessment (CIWA)⁴⁶. Exclusionary mental health conditions will be assessed using the MINI Neuropsychiatric Interview for DSM-5⁴⁷. Subjects will undergo laboratory testing that includes liver and renal function tests, glucose, serum lipase, complete blood count, urine toxicology and a urine pregnancy test for women of child bearing potential.

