Subjects will receive either a 5 mcg dose of immediate release exenatide or a sham injection. The 5mcg dose of exenatide is approved as the first dose to be administered to patients at the start of their treatment with this drug for FDA-approved indications. The sham injection will be a needle stick insulin syringes with pre-affixed needles as a sham syringe. Note that the volume of fluid injected for a 5mcg dose is only 0.02ml. We do not expect that subjects will sense this volume of fluid (or lack thereof) during the injection. Subjects will be shielded from seeing the injection to maintain the blind. The individual who administers medication will not participate in subject evaluation to maintain the study blind. The study medication will be administered subcutaneously 30 minutes prior to the priming dose of alcohol. Peak plasma concentrations of exenatide injected as 5 mcg dose are seen at about 90-120 minutes after subcutaneous administration of this drug and its terminal half-life is 2.4 hours^{13,50}. A 5 mcg dose of exenatide injected prior to the administration of oral glucose was found to enhance cerebral glucose metabolic rate in brain regions implicated in the regulation of appetite and food reward among subjects with impaired glucose metabolism³³. These effects were observed 90 minutes after the administration exenatide. The 5 mcg dose of exenatide was found to prevent elevation in blood glucose levels and the rate of glucose absorption after the administration of oral glucose³³.

The Effects of Exenatide, a GLP-1 Agonist, on Alcohol Self-Administration in Heavy Drinkers
Version 1.8 10.5.20

The priming drink will be given no more than 30 minutes after study drug is administered (see Figure 2 for alcohol challenge timeline). Subjects will have five minutes to consume a single priming dose of alcohol. After a 40-minute observation period, subjects will begin the alcohol self-administration Blocks 1 and 2. The alcohol self-administration trials will be conducted in a human laboratory designed to simulate a typical living room. The human laboratory is a room furnished with a lounge chair, side table, and television which allows access to popular streaming entertainment (e.g., Netflix, YouTube). A small unobtrusive camera is in the room to allow for monitoring and video recording without study staff being present.

Priming dose.

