There will be a 7-14 day washout period between alcohol Challenge Trial #1 and Trial #2. Based on the known half-life of exenatide, all of the medication will be cleared within 2 days. The washout may extend up to 14 days to provide flexibility in scheduling of Trial #2. After the second alcohol self-administration trial has been completed subjects will receive a copy of the

Figure 2: Alcohol Self-Administration Procedure

Study drug Study drug administered 30 minutes prior to priming dose	Priming Dose 5 minutes Drink mixed to achieve BAC= 0.03g/dl	Absorption 40 minutes BAC measured in 10-minute intervals	Self-Administration Blocks 1 & 2 60 minutes each 4 drinks per block Each drink mixed to raise BAC 0.0125 g/dl
--	---	---	---

The Effects of Exenatide, a GLP-1 Agonist, on Alcohol Self-Administration in Heavy Drinkers
Version 1.8 10.5.20

NIAAA publication *Rethinking Drinking*⁴⁸ and will be encouraged to review rethinking drinking materials online. Subjects will be compensated up to \$448 for completion of all study activities. Subjects will receive a reimbursement of \$50 for the screening visit, \$150 for alcohol Challenge Trial #1, \$150 for alcohol Challenge Trial #2. Subjects will receive a \$50 bonus for completing both alcohol Challenge Trials. Subjects may receive up to \$48 dollars in payments for drinks not consumed during the two alcohol self-administration Trials. Subjects who report no recreational drug use other than marijuana at the time of phone screening but then test positive for recreational drug use other than marijuana at the first in-clinic visit will not be reimbursed. Subjects will be informed of this policy at the time of telephone screening. This measure is in place to prevent subjects from lying about no recreational drug use in order to receive compensation for a single visit in this study.

10 Assessment of Safety and Data Safety Monitoring Plan (DSMP)

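### No adverse-event contact is scheduled after Trial 2, so events that begin after discharge from that visit are recorded only if the subject calls

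*Combined protocol and SAP*

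**What the plan says.** Section 10.2 sets the window, "Adverse events will be monitored from the time of study enrollment until the end of participation", and the method, "Adverse event monitoring will be conducted at each study visit from the time of consent". Section 9 defines what a subject goes through: "Study participation is comprised of a baseline assessment, alcohol challenge Trial #1, and alcohol challenge Trial #2". In Appendix A the AE and TLFB rows are ticked at baseline, Trial 1 and Trial 2, and no column follows.

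Between the two challenges, Section 9 states: "There will be a 7-14 day washout period between alcohol Challenge Trial #1 and Trial #2". Anything that happens after the Trial 1 injection is thus asked about when the subject returns for Trial 2. One of the two randomized sequences receives exenatide in Trial 2.

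Two provisions reach past the last procedure:

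- Section 10.2 continues to assess a serious event or unanticipated problem that is already under way when the subject finishes.
- Section 6.1, in its opening and again under protections against risks, tells subjects to contact staff about health changes once study medication has started. It gives them a wallet card with a 24/7 number and sets no end date. Section 10.2 describes the card as serving the time before the next planned visit.

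On pharmacology, Section 9 says: "Peak plasma concentrations of exenatide injected as 5 mcg dose are seen at about 90-120 minutes after subcutaneous administration". It gives a terminal half-life of 2.4 hours and, to justify the washout, adds: "Based on the known half-life of exenatide, all of the medication will be cleared within 2 days".

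Section 6.1 also names a risk that lies after the visit: "There is a potential risk of increased alcohol consumption following the alcohol self-administration experiment". Section 10.2 opens by committing to monitor the Section 6.1 risks together with unknown ones.

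**The concern.** The two challenge visits are alike in dosing and procedure but not in safety follow-up. After Trial 1, someone asks the subject about adverse events and drinking a week or two later. After Trial 2, nobody does. An event that begins after discharge from Trial 2 falls outside the provision for events already under way, so its recording depends on the subject choosing to call.

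The stake is completeness. Section 10.3 asks for a summary of events at continuing review, with a statement about their overall pattern. Section 10.4 suspends enrollment on a single qualifying serious event. Both would draw on 7-14 days of solicited follow-up after one injection and only the hours of the visit after the other. Increased drinking after the challenge cannot be seen within the Trial 2 visit at all. For that risk the gap covers every subject who completes Trial 2, whichever injection was given there.

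**Working it through.** **1. The protocol's clearance figure.** Half-life 2.4 h (Section 9). 48 h / 2.4 h = 20 half-lives, and 2^(-20) is about 0.000001. Clearance within 2 days follows from the stated half-life with a wide margin. At 12 h, five half-lives from injection, 2^(-5) = 3.1% remains, so about 97% is gone.

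**2. Earliest discharge.** Section 9 and its Figure 2 give 30 min from injection to priming drink, 5 min to drink it, 40 min absorption and two 60-min blocks: 30 + 5 + 40 + 60 + 60 = 195 min = 3.25 h after injection.

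Section 9 releases subjects once BAC is below 0.04 g/dl and they are not behaviorally impaired. From the start of the priming drink to the end of Block 2 is 165 min = 2.75 h. With k drinks taken and the Section 6.1 elimination range of 0.010 to 0.020 g/dl per hour, approximate BAC is 0.03 + 0.0125k - 2.75 x rate:

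- At 0.010: 0.0025 + 0.0125k, which is below 0.04 for k up to 2.
- At 0.020: -0.025 + 0.0125k, which is below 0.04 for k up to 5.

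A subject who drinks little can therefore meet the BAC condition as soon as Block 2 ends.

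**3. Drug remaining then.** Assume a single-exponential decline from a peak at 90 or 120 min, with a half-life of 144 min:

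- Peak at 120 min: 195 - 120 = 75 min after peak; 0.5^(75/144) = 0.70.
- Peak at 90 min: 195 - 90 = 105 min after peak; 0.5^(105/144) = 0.60.

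**4. Latest discharge.** Take the top of the Section 6.1 range of estimated peak BAC, 0.13 g/dl, falling at 0.010 per hour from the end of Block 2. The wait is (0.13 - 0.04) / 0.010 = 9 h, so release is at 12.25 h. This is an outer bound, because 0.13 = 0.03 + 8 x 0.0125 allows for no elimination during the session.

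**5. Share of the 2 days that lies after discharge.** (48 - 3.25) / 48 = 93% at the earliest release and (48 - 12.25) / 48 = 74% at the latest.

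**6. Exposures affected.** Section 12.2 plans 36 randomized and 28 completers. With equal sequences (assumed), 18 of 36 or 14 of 28 exenatide exposures fall in Trial 2.

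**7. What zero delayed events would show.** Exact one-sided 95% upper bound = 1 - 0.05^(1/n), counting only exposures with solicited follow-up:

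| Basis | Half followed | All followed |
|---|---|---|
| 36 randomized | n = 18: 15.3% | n = 36: 8.0% |
| 28 completers | n = 14: 19.3% | n = 28: 10.1% |

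The two-sided version, 1 - 0.025^(1/n), gives 18.5% and 9.7% for n = 18 and 36.

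**8. Length of participation.** Up to 14 days to Trial 1 plus up to 14 days of washout is 28 days, as Section 9 states. Section 2 says: "Each subject will complete up to 4 clinic visits over a period of up to 38 days of participation". A baseline split over two days (Appendix A) explains the fourth visit. Nothing explains the other 38 - 28 = 10 days, and no text assigns them to a follow-up contact.

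**The case against.** The case for leaving the plan alone is reasonable. This is one injection, at the labelled starting dose, of an approved drug in a laboratory crossover. Subjects are told to call with any health concern, and that instruction has no end date. On the stated half-life little drug is left by 12 hours, so the 60-70% figure describes only the earliest exit. Section 6.1 calls increased drinking afterwards rare, on the strength of studies with 6-week and 3-month follow-up, which a short call does not match. Section 12 plans no analysis of adverse-event rates, so no planned estimate changes.

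Much of this stands, and it rules out several stronger readings that a reader might infer:

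- *That events after Trial 2 have no route into the record.* The call line is a route. The reporting clocks in Section 10.3 start when the investigator learns of an event, and the serious-event rule in Section 10.4 has no time window. A reported event can feed both.
- *That collection formally ends at Trial 2.* Section 10.2 refers to the end of participation without defining it, and Sections 2 and 9 differ on its length. The end point is an inference from the visit schedule.
- *That pancreatitis, allergic reaction or vomiting is known to begin after discharge from one such dose.* The documents do not say so.
- *That the 2-day figure is a risk window the plan ignores.* It is given only to justify the washout.
- *That the exenatide-sham comparison is biased.* With balanced sequences, exenatide and sham given in Trial 2 lose follow-up equally.

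The objection does not remove the difference between the trials. A call line depends on the subject recognizing an event and choosing to report it. It also yields no drinking record, which Appendix A does collect after Trial 1.

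**Conclusion.** The gap is real and modest. Injections in Trial 1 have a solicited AE and TLFB assessment 7-14 days later, and injections in Trial 2 have none after discharge. The consequence is under-recording of events that begin after the subject leaves, for about half of the exenatide exposures. As a yardstick, the one-sided 95% bound after zero delayed events is 15.3% instead of 8.0%.

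This rests on four assumptions: equal sequences; participation ending with the Trial 2 visit; few unsolicited reports; and, for the bounds, all 36 randomized subjects receiving exenatide, with those who received it in Trial 1 returning. It is a cheap improvement to safety ascertainment. It is not a flaw in the primary comparison.

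**What to change.** In Section 10.2 and Appendix A:

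- Add one telephone AE and TLFB contact by existing staff after each subject's last injection. Include subjects who stop after Trial 1, who would otherwise be missed. Place it at least 2 days after the injection, preferably at 7-14 days to match the interval after Trial 1.
- Define the end of participation, for AE collection, as that contact.
- Reconcile the 28-day and 38-day figures in Sections 9 and 2, and restate the length with the contact included.
- Summarize AEs by treatment over the same post-injection window in both trials.

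The cost is a protocol amendment and about 36 short calls, some of which will go unanswered. Participation lengthens by up to 14 days, for example from 28 to 42 on the Section 9 figure. No dose, challenge procedure or endpoint changes. A call at this interval would not reproduce the 6-week to 3-month drinking follow-up cited in Section 6.1, but it would put the two trials on the same footing.

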10.3 Reporting Plans

The Principal Investigator at BMC/BU Medical Campus will report Unanticipated Problems, safety monitors' reports, and Adverse Events to the BMC/BU Medical Center IRB in accordance with IRB policies:

- Unanticipated Problems occurring at BMC/BU Medical Campus involving a fatal or life-threatening event will be reported to the IRB within 2 days of the investigator learning of the event.
- Unanticipated Problems occurring at BMC/BU Medical Campus not involving a fatal or life-threatening event will be reported to the IRB within 7 days of the investigator learning of the event.
- Reports from safety monitors with recommended changes will be reported to the IRB within 7 days of the investigator receiving the report.
- Adverse Events (including Serious Adverse Events) will be reported in summary at the time of continuing review, along with a statement that the pattern of adverse events, in total, does not suggest that the research places subjects or others at a greater risk of harm than was previously known.
- Reports from safety monitors with no recommended changes will be reported to the IRB at the time of continuing review.

